6.2.1.1 Permitted concomitant therapy requiring caution and/or action

Investigators may prescribe concomitant medications or treatments deemed necessary to provide adequate supportive care except for those medications identified as "prohibited" as listed in Table 6-3. Specifically, subjects should receive full supportive care during the study, including treatment with antibiotics, anti-emetics, anti-diarrheals, analgesics, and other care as deemed appropriate, and in accordance with their institutional guidelines. In addition to the background asthma medications and rescue medications described in Section 6.1.2, the following concomitant medications related to asthma/allergy treatment are permitted from screening through the follow-up period.

	Table 6-1	Medications	allowed under	certain	conditions
--	-----------	--------------------	---------------	---------	------------

Class of medication	Condition
Topical corticosteroids for the treatment of eczema	In recommended doses and dosage regimens
Intra-nasal corticosteroids	Stable dose for at least 1 month prior to Screening. In the case of as needed, provided an established pattern of use has been documented.
Systemic corticosteroids	To treat asthma exacerbations
Topical antihistamines	In recommended doses and dosage regimens
Oral antihistamines	Stable dose for at least 1 month prior to Screening and throughout the trial.
	In the case of as needed, provided an established pattern of use has been documented
Topical, nasal, and/or ocular formulations of cromones	In recommended doses and dosage regimens
Maintenance immunotherapy for allergies	Stable dose for at least 3 months prior to run-in visit and unchanged throughout study treatment.
COVID-19 vaccination	At least one week before an in-clinic visit

Table 6-2 Medications to be withheld prior to spirometry

Class of medication	Last dose prior to spirometry
Short-acting β ₂ -agonists (SABA)	≥ 6 hours
Long-acting β_2 -agonists (LABAs) given twice daily	≥ 24 hours
ICS-Formoterol given PRN	≥ 24 hours
LABAs given once daily (e.g. vilanterol, indacaterol)	≥ 36 hours
Long-acting muscarinic antagonists (LAMAs e.g. tiotropium)	≥ 7 days
Fixed-dose combinations of LABA and ICS given twice daily	≥ 24 hours
Fixed-dose combinations of LABA and ICS given once daily	≥ 36 hours
Fixed-dose combinations of LABA and LAMA and ICS given once daily or twice daily.	≥ 2 days

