The treatment of asthma exacerbations including the initiation of systemic corticosteroids should be done according to investigator's or treating physician's medical judgement and should be in line with their institutional, national and international recommendations. If systemic corticosteroids are required, a patient may return to the study assessments after successfully completing an Oral Corticosteroid (OCS) taper. If patients require treatment with systemic steroids longer than 3 weeks, including taper, or chronic systemic steroid administration, they must be discontinued from treatment.

If indicated for the treatment of an adverse event, including asthma exacerbation, any treatment (including medications in Table 6-3) deemed necessary by treating physician for the safety of the patient is allowed from the start of the event until the event is resolved. If it is transitioning to chronic treatment, the investigator should discuss with Novartis Medical Monitor. Patients may NOT self-medicate (other than administration of rescue medication) or adjust therapy without permission/guidance from treating physician.

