6.2.2 Prohibited medication

The specified minimum washout periods prior to the run-in are described in Table 6-3. Use of the treatments displayed in Table 6-3 is NOT allowed after the beginning of run-in (unless for the treatment of adverse events and asthma exacerbations). Each concomitant drug must be individually assessed against all exclusion criteria and the tables below to see if it is allowed. If in doubt, the investigator must contact the Novartis medical monitor or designee before randomizing a patient or allowing a new medication to be started. Medications must be assessed for adherence to the indication and other inclusion/exclusion criteria.

Class of medication	Minimum cessation prior to Run-In ^{1,2}
Other investigational drugs	30 days or 5 half-lives, whichever is longer
Live attenuated vaccine*	2 days
Inactivated influenza vaccination, pneumococcal vaccination or any other inactivated vaccine*	2 days
Short-acting anticholinergics (SAMA)	6 hours
Long acting muscarinic antagonists (LAMAs)*	7 days
Fixed combinations of short-acting β_2 agonists and short-acting anticholinergics (SABA/SAMA)	12 hours
Xanthines*	7 days
Leucotriene Receptor Antagonists (LTRAs) and leucotriene synthesis inhibitors*	7 days
Systemic mast cell stabilizers (e.g., cromoglycate, nedocromil, ketotifen)*	7 days
Oral corticosteroids	6 weeks
Short-acting, intra-articular, intramuscular, intravenous corticosteroid	6 weeks
Long acting, intra-articular, intramuscular depot corticosteroids	3 months and 2 weeks
Monoclonal antibodies for the treatment of asthma (e.g. omalizumab, mepolizumab, benralizumab etc.) (investigational or approved)	5 half-lives or 6 months, whatever is longer
Other anti-TSLP drugs (investigational or approved)	Not permitted
Methotrexate, gold salts, cyclosporine, troleandomycin, azathioprine, other immunomodulator drugs or immunomodulatory monoclonal antibodies	6 months

Table 6-3Prohibited medication

¹ This table is not considered all-inclusive. Medications should be assessed for adherence to the indication and other inclusion/exclusion criteria

² These medications are also prohibited if administered for other indications

*these medications can be used again in the follow up period

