12.4.3 Handling of missing values/censoring/discontinuations

Despite all attempts to ensure complete follow-up for all patients, some patients may not be followed for pre-dose FEV1 for the whole planned study duration.

The FEV1 value analyzed at each post-baseline visit is based on the average of the two FEV1 assessments taken at approximately 45 minutes and approximately 15 minutes prior to the dosing of study drug at clinic visits. Since the estimand is related to an effect outside of rescue med intake, spirometry measurements within 6 hours of rescue medication, within 7 days of intake of systemic corticosteroid use, or within 3 months of a single depot corticosteroid injection, or within 24 hours of background medication use, or within 48 hours of LAMA use will be set to missing. In cases where one of the two values is missing, the remaining non-missing value will be taken as pre-dose FEV1. If both values are missing, then their pre-dose FEV1 will be regarded as missing at that visit.

For the primary analysis, only on-treatment data (from date of first randomized dose up to 1 day after date of last randomized dose) will be used as the estimand specifies a hypothetical on-treatment effect. Missing on-treatment data will not be explicitly imputed as the MMRM implicitly imputes missing data assuming the missing at random (MAR) mechanism.

The imputation procedures related to the pre-dose FEV1 supportive analyses (Section 12.4.4) are "jump-to-reference" (J2R) and MAR (Carpenter et al 2013). The imputations will be based on all available data (i.e. from all scheduled timepoints) using all covariates as specified in the MMRM. For J2R, only placebo (reference) data will be used. For MAR, data from the same treatment arm will be used for building the imputation model. Imputation of intermittent missing observations before treatment discontinuation will be carried out following a MAR mechanism for all treatment arms. Additional details will be available in the SAP.

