#### 2.5.1 **Primary endpoint**

The primary estimand, defined below, quantifies a hypothetical on-treatment effect during stable periods (i.e. outside of periods of acute disease worsening requiring additional asthma medications). This estimand targets the maximum treatment effect for CSJ117 and allows selection of the best dose for those who take it for 12 weeks.

- **Population**: adult patients with inadequately controlled asthma on medium or high dose ICS/LABA, alone or with up to two additional asthma controllers (LTRA, LAMA or theophylline)
- Variable: Average change from baseline in pre-dose FEV1 after 8 and 12 weeks of treatment
- **Treatment**: CSJ117 or placebo

- Intervention effect of interest: Effect of interventions initiated at randomization during stable periods and that would have been observed had all patients remained on their assigned treatment for 12 weeks, with the following post-randomization events accounted for by assessing:
  - Intake of non-study drug with effect on FEV1: the effect outside of periods of worsening disease that necessitate such non-study drug
  - Discontinuation of study treatment due to any reason: hypothetical value of the average between Week 8 and Week 12 pre-dose FEV1 had the patients not stopped the study treatment
  - The case where patient received treatment different from the assigned treatment: hypothetical value of the average between Week 8 and Week 12 pre-dose FEV1 had the patient remained on the assigned treatment for 12 weeks
- Summary measure: mean difference between CSJ117 and placebo

This estimand is considered appropriate for a dose finding trial in order to obtain a clear dose response signal and understand the maximum potential effect of the drug.

The baseline value is defined as the average of the values taken approximately 2 hours 45 minutes and 2 hours 15 minutes prior to the first dose of double-blind treatment at Day 1. If one of the two values is missing (or is not confirmed to be pre-dose) then the remaining non-missing value will be taken as the baseline. If both values are missing (or are not confirmed to be pre-dose), then the measurements taken at the run-in visit will be used as the baseline.

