#### 2.5.3 Handling of missing values/censoring/discontinuations

Despite all attempts to ensure complete follow-up for all patients, some patients may not be followed for pre-dose  $FEV_1$  for the whole planned study duration.

The FEV1 value analyzed at each post-baseline visit is based on the average of the two FEV1 assessments taken at approximately 45 minutes and approximately 15 minutes prior to the dosing of study drug at clinic visits. Since the estimand is related to an effect outside of periods of acute disease worsening requiring additional asthma medications, spirometry measurements taken within 6 hours of rescue medication, 7 days of intake of systemic corticosteroid use, 3 months of a single depot corticosteroid injection, 24 hours of background medication use, and/or 48 hours of LAMA use will be set to missing. In cases where one of the two values is missing, the remaining non-missing value will be taken as pre-dose FEV1. If both values are missing, then their pre-dose FEV1 will be regarded as missing at that visit.

For the primary analysis, only on-treatment data (from date of first dose of double-blind treatment up to 1 day after date of last dose) will be used as the estimand specifies a hypothetical on-treatment effect. Missing on-treatment data will not be explicitly imputed as the MMRM implicitly imputes missing data assuming the missing at random (MAR) mechanism.

The imputation procedures related to the pre-dose  $FEV_1$  supportive analyses (Section 2.5.4) are "jump-to-reference" (J2R) and MAR (Carpenter et al 2013). The imputations will be based on all available data (i.e. from all scheduled timepoints) using all covariates as specified in the MMRM. For J2R, only placebo (reference) data will be used. For MAR, data from the same treatment arm will be used for building the imputation model. Imputation of intermittent missing observations before treatment discontinuation will be carried out following a MAR mechanism for all treatment arms. Additional details are provided in Section 5.5.

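### FEV1 is dropped only within 48 hours of any LAMA use, so values taken 2 to 7 days after a stand-alone LAMA stay in the primary analysis despite the protocol's 7-day withholding time

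*SAP*

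**What the plan says.** SAP 2.5.3 and protocol 12.4.3 set FEV1 to missing if it was measured too soon after certain drugs. The windows are 6 hours for rescue medication, 7 days for systemic corticosteroid, 3 months for a single depot injection, 24 hours for background medication and 48 hours for LAMA. The SAP wording ends "24 hours of background medication use, and/or 48 hours of LAMA use will be set to missing" and the protocol wording ends "or within 24 hours of background medication use, or within 48 hours of LAMA use will be set to missing". Neither separates LAMA given alone from LAMA in a combination inhaler.

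Protocol Table 6-2 (section 6.2.1.1) sets how long each drug is withheld before spirometry, and it does make that separation. The row "Long-acting muscarinic antagonists (LAMAs e.g. tiotropium") requires at least 7 days. The row "Fixed-dose combinations of LABA and LAMA and ICS given once daily or twice daily" requires at least 2 days. The row "Fixed-dose combinations of LABA and ICS given twice daily" requires at least 24 hours.

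Table 6-3 (section 6.2.2) lists "Long acting muscarinic antagonists (LAMAs") with a 7-day minimum cessation before run-in and bars them afterwards, except to treat adverse events and exacerbations. Section 6.2.1.1 makes the same exception, limited to the time that the event is ongoing: "any treatment (including medications in Table 6-3) deemed necessary by treating physician for the safety of the patient is allowed". For non-study drugs that affect FEV1, the estimand in SAP 2.5.1 targets "the effect outside of periods of worsening disease that necessitate such non-study drug".

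**The concern.** The SABA window (6 hours) and the background ICS-LABA window (24 hours) equal the Table 6-2 withholding times. The LAMA window equals only the combination row. From run-in onward the background is fixed as fluticasone/salmeterol (protocol 6.1.2.2), so a LAMA added during treatment would more naturally be a separate inhaler, to which the 7-day row applies.

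A value kept 2 to 7 days after a stand-alone LAMA may still carry bronchodilation that is not due to study drug. If placebo patients need LAMA more often, this raises the placebo mean and shrinks the estimated effect of CSJ117. If the use falls in an active arm, it enlarges that arm's estimate. The FEV1 value defined in SAP 2.5.3 also appears to feed the supplementary analysis in SAP 2.5.4.

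**Working it through.** **Windows side by side**

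| Drug | Analysis window (SAP 2.5.3, protocol 12.4.3) | Withholding time (protocol Table 6-2) | Uncovered |
|---|---|---|---|
| Rescue SABA | 6 h | at least 6 h | 0 h |
| Twice-daily ICS-LABA | 24 h | at least 24 h | 0 h |
| ICS-LABA-LAMA combination | 48 h | at least 2 days = 48 h | 0 h |
| Stand-alone LAMA | 48 h | at least 7 days = 168 h | 168 − 48 = 120 h (5 days) |

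**Which values fall in the gap**

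- A patient still taking LAMA daily is inside 48 hours, so the value is already removed.
- A permanent user of a prohibited drug must stop study treatment (protocol 9.1.1), and later values leave the on-treatment primary analysis.
- Protocol 8.6.4 defines every non-fatal exacerbation by systemic corticosteroid treatment and defers scheduled spirometry until it has resolved. If LAMA stops with or before the steroid course, the 7-day steroid window already covers the disputed days.
- What remains is a stand-alone LAMA given for an adverse event or worsening without systemic corticosteroids, and stopped 2 to 7 days before the Week 8 or Week 12 visit. For recent SABA or background ICS-LABA, protocol 6.1.2.1 and 6.1.2.2 also require the test or visit to be rescheduled. I found no such instruction for LAMA.

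**Size**

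Inputs from the documents: 335 patients enrolled (SAP 1.1), 2:1:1:1:2:2 allocation, target effect 120 mL, and variances 0.1461 and 0.1456 with covariance 0.1163 (SAP 3). The stated SD reproduces to rounding: √((0.1461 + 0.1456 + 2 × 0.1163)/4) = √0.131075 = 0.3620 L, against 0.3622 L in the plan.

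Assumed inputs, because the documents give neither: k = 1 to 3 affected placebo patients, and a residual effect r = 50 to 150 mL.

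- Placebo n = 335 × 2/9 = 74.4.
- With one of the two visits affected, the Week 8/12 average moves by about half: shift = k × r / (2n).
- Low end: 1 × 50 / (2 × 74.4) = 0.34 mL. High end: 3 × 150 / (2 × 74.4) = 3.02 mL.
- Share of the 120 mL target: 0.34/120 = 0.3% to 3.02/120 = 2.5%.
- Approximate SE for placebo versus 8 mg, ignoring missing data: 362.2 × √(2/74.4) = 59.4 mL. High end as a share: 3.02/59.4 = 5.1%.
- If the same patients were affected at both visits the shift doubles, to 0.7 to 6.0 mL. A transient user would then have to fall in a 5-day gap twice, four weeks apart.

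**The case against.** The strongest reply is that nothing obliges the analysis windows to equal Table 6-2, which governs what patients withhold before a planned test. The corticosteroid windows in the same sentence are not in Table 6-2 at all, and they are shorter than the Table 6-3 washouts (6 weeks for oral; 3 months and 2 weeks for depot). The protocol itself accepts 2 days for one form of LAMA. If LAMA is stopped when the event resolves, a value more than two days later lies outside the period of worsening, so keeping it follows the estimand's wording. A wider window also discards observed data and leans more on MAR.

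Much of this stands. The 48 hours is an unexplained design choice, not a contradiction, and a flat 7 days for all LAMA use would create a new mismatch with the combination row. But resolution of the event does not show that the drug effect has gone. For stand-alone LAMA the protocol's own measure of that is 7 days, and the other bronchodilator windows follow the table.

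A reader might also infer that every affected value is compared with a baseline at least 35 days free of LAMA (7 days of washout plus 28 days of run-in). The documents do not guarantee this: Table 6-3 drugs may be used for adverse events and exacerbations during run-in, and patients with a run-in exacerbation stay in with run-in extended to 8 weeks.

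**Conclusion.** The mismatch is real and confined to stand-alone LAMA. Its reach is narrow: short use without systemic corticosteroids, ended 2 to 7 days before a Week 8 or Week 12 visit. Under the assumed inputs the placebo mean moves by about 0.3 to 3 mL, small against the 120 mL target and against a standard error near 59 mL. Both the number of patients and the residual effect are assumptions.

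A reader might go further and infer that the primary result is materially biased toward no effect. The documents do not support that. They give no frequency of LAMA use by arm, and the direction is open: residual bronchodilation raises FEV1, a recent worsening may lower it, and use in an active arm works the other way from use on placebo. This is an optional correction, worth making because it costs little.

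**What to change.** In SAP 2.5.3, set FEV1 to missing within 7 days of stand-alone LAMA use and keep 48 hours for ICS-LABA-LAMA fixed-dose combinations, as in Table 6-2. Report, by arm and visit, the number of FEV1 values taken more than 48 hours and up to 7 days after stand-alone LAMA. If there are none, the matter closes. If there are any, rerun the primary MMRM and MCP-Mod under the 48-hour window as a sensitivity analysis. If treatment codes are already open, keep 48 hours as primary and report 7 days as the sensitivity analysis.

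The cost is a short change to the SAP text, a programmed window that separates stand-alone from combination LAMA, one count table and at most one rerun. Concomitant medications are already collected (protocol 6.2.1), so sites and patients see no change. The downside is that a few more values are set to missing and handled under MAR.

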#### 2.5.4 Supportive analyses

A supplementary analysis will be performed that quantifies the treatment effect in all randomized patients during stable periods (i.e. outside of periods of acute disease worsening requiring additional asthma medications) with an adherence to treatment like we would see in clinical practice in a world without COVID-19, with the following post-randomization events accounted for by assessing:

a. Intake of non-study drug with effect on  $FEV_1$ : the effect outside of periods of worsening disease that necessitate such non-study drug.

b. Discontinuation of study treatment due to any reason not covered in bullet c below: actual off-treatment value. If no data was retrieved after study treatment discontinuation, missing data will be multiply imputed based on placebo arm data: J2R assumption for the CSJ117 arms and MAR assumption for placebo arm.

For business use only

c. Discontinuation of study treatment due to early termination of the study by sponsor or any COVID-19 related reason: hypothetical value of the average between Week 8 and Week 12 predose  $FEV_1$  had the patients not stopped the study treatment.

Results will be presented similarly to those of primary analyses. Details are provided in Section 5.5.

The subgroup analyses (subgroups defined in Section 2.2.1) will be explored for the primary estimand and the same MMRM as described for the primary analysis with the additional term of subgroup factor (if not already included in the model), the two-way interaction term of subgroup and treatment, and the three-way interaction term of subgroup, treatment, and visit. In case of analyses on subgroups with extremely imbalanced sample sizes, the subgroup levels can be combined, if appropriate, while fitting the analysis model. The point estimate and 95% CI for treatment differences between CSJ117 doses and placebo for each subgroup will be provided.

#### 2.6 Analysis of the key secondary objective

There is no key secondary objective defined in the protocol.

#### 2.7 Analysis of secondary efficacy objective(s)

No multiplicity adjustment will be carried out for secondary analyses described below. In addition, the treatment effect of CSJ117 compared to placebo that would have been observed had all patients remained on their assigned treatment will be estimated. Only on-treatment data will be used.

All analysis of secondary efficacy endpoints will be performed on the FAS.

Missing data for any reason will not be explicitly imputed and will be handled by the respective mixed effects model which implicitly imputes missing data assuming MAR.

Details on statistical models are provided in Section 5.5.

#### 2.7.1 Secondary endpoints

#### 2.7.1.1 FeNO

The average change from baseline in Fractional exhaled Nitric Oxide (FeNO) at Week 8 and Week 12 will be analyzed using the same MCP-Mod approach described for the primary analysis of the primary endpoint. The change from baseline in FeNO will be analyzed using a similar MMRM (including all scheduled post-baseline visits with FeNO data) on the FAS as used for the primary analysis but will include baseline FeNO instead of baseline FEV1. The estimated treatment difference (CSJ117 – placebo) at each visit will be reported as well as the average between Week 8 and Week 12 along with the associated 95% confidence interval.

#### 2.7.1.2 ACQ-5

The ACQ-5 measures asthma symptom control and consists of 5 items (questions) on symptom assessment. Patient recall is one week.

For business use only

All 5 questions of the ACQ-5 are equally weighted. Items are scored along a 7-point response scale, where 0 = totally controlled and 6 = severely uncontrolled.

The total score is calculated as the mean of all five questions.

The average of mean change from baseline in ACQ-5 at Week 8 and Week 12 will be analyzed using the same MMRM (including all scheduled visits with ACQ data) on the FAS as used for the primary analysis but will include baseline ACQ-5 instead of baseline FEV1. The estimated treatment difference (CSJ117 – placebo) at each visit will be reported as well as the average between Week 8 and Week 12 along with the associated 95% confidence interval.

The proportion of patients who achieve an improvement of at least 0.5 in ACQ-5 (i.e. decrease of ACQ-5 score of at least 0.5 from baseline) at post-baseline visits will be analyzed using a repeated measurements logistic regression. The model will inlcude the same terms as for the MMRM analysis of the primary variable with baseline ACQ-5 instead of baseline FEV1. The estimated adjusted odds ratios at each visit will be displayed along with the associated 95% confidence intervals.

